3.3 Study design

This is a prospective cohort study employing a medical device (the AVA bracelet) as a monitoring tool. The GAPP study is already running since June 2010 and, after the baseline exam has been conducting follow-up visits every 3-5 years. Currently, the second follow-up period is being conducted. Due to the COVID-19 pandemic, the regular follow-up has been suspended. The study collective is very well described.

3.4. Study intervention

As soon as possible after ethical approval (within 1 week), study participants are offered an AVA bracelet. They will be asked to wear the AVA bracelet during the night until the study will be terminated. Temperature, breath rate, pulse rate and movings are recorded. Information on COVID-19 specific health status is collected at study start and symptomatic patients will be diagnosed for COVID-19, as recommended by national guidelines. At the end of the study blood will be drawn for serological analysis of anti-SARS-CoV2 antibodies.

4 STUDY POPULATION AND STUDY PROCEDURES

4.1 Inclusion and exclusion criteria, justification of study population

The GAPP study is a population based national cohort including 2170 study participants aged 25 to 41 at baseline. This number relates to about 32% of the whole population. Since the study was started to enrol participants from 2010, the study participants are now 35 to 51 years old ⁸.

The GAPP study (study homepage www.blutdruck.li) is an ongoing national cohort study done in the principality of Liechtenstein with a cooperation from the University Basel, Private University Liechtenstein, McMaster University Hamilton, and the labormedizinische zentrum [name] in Liechtenstein. Between 2010 and 2014 all inhabitants of Liechtenstein aged 25-41 years old were asked to participate in the study, and 2170 could be enrolled. The aim of the study is to identify the determinants for the development of hypertension and other cardiovascular risk factors. A large number of baseline characteristics and health information was collected in all participants. Several blood, urinary and genetic markers were collected. By ongoing follow-up we collect information on changes in health information and other characteristics are collected. Currently the second follow-up cycle is ongoing.

GAPP is very well established scientifically. More than 30 scientific manuscripts have been published so far, some of them in major international journals ⁸⁻⁴¹. Therefore, the quality of the data collection is well recognized. In summary, the GAPP study provides a unique platform that would allow rapid evaluation of a promising medical device that has the potential to alleviate the suffering through the current COVID-19 pandemic.

The choice of the study population is ideal, as the organization is already in place, the study participants are already enrolled. With such a setting, the important and urgent study question can be addressed immediately.

Inclusion criteria:

- Participant of the GAPP study
- Providing consent to the present study

Exclusion criteria:

- Inability to provide informed consent

It is not planned to include vulnerable participants into the study.

After a first phase of including participants from the GAPP-study, we eventually might attain a sample size of 5000 participant by onboarding additional participants. For this second phase, we will seek separate ethical approval.

4.2 Recruitment, screening and informed consent procedure

The GAPP study department harbors 6 collaborators performing the study visits of the study participants onsite at the GAPP study facility ([name]) in Vaduz, Liechtenstein. The department has 4 consultation rooms and 3 office rooms. The proximity to the consultation rooms of the labormedizinische zentrum [name] allows for rapid scale-up of activities. Since the study is up and running and has a very good reputation within the study cohort and the whole country, starting the evaluation of the AVA watch in the COVID-19 pandemic is readily available. According to the world rankings, Liechtenstein is one of the countries with the highest incidences of COVID-19 (1582 cases per million persons, first case 2. March 2020), but on the other hand also has one of the highest testing frequencies for SARS-CoV-2 (2.75 percent of the whole population tested by March 29th 2020). Proximity of laboratory and study center, nationwide coverage of laboratory analysis, running national cohort, international cooperation, government support are all success factors for the envisaged project.

Participants already provided informed consent for participation in the GAPP study. As the study organization has an up-to-date address database, study participants are contacted by letter, email or telephonically. They will receive the participant information and called in into the study center upon stating their will to participate, where the AVA bracelet will be distributed. They will be offered opportunity to ask questions before providing informed consent by telephone, email, or at the occasion of device distribution, namely before the AVA bracelet will be distributed.

The investigators will explain to each participant the nature of the study, its purpose, the procedures involved, the expected duration, the potential risks and benefits and any discomfort it may entail. Each participant will be informed that the participation in the study is voluntary and that he or she may withdraw from the study at any time and that withdrawal of consent will not affect his or her subsequent medical assistance and treatment.

The participant will be informed that his or her medical records may be examined by authorised individuals other than their treating physician.

All participants for the study will be provided a participant information sheet and a consent form describing the study and providing sufficient information for participant to make an informed decision about their participation in the study. The time between obtaining the study information and starting the distribution of AVA bracelets is at least 1 day.

The formal consent of a participant, using the approved consent form, will be obtained before the participant is submitted to any study procedure. The consent form will be signed and dated by the investigator or his designee at the same time as the participant sign. A copy of the signed informed consent will be given to the study participant, if requested. The consent form will be retained as

part of the study records. The informed consent process is documented in the participant database and any discrepancy to the process described in the protocol must be explained. No compensation is offered to study participants. They can keep the AVA bracelet after terminating the study.

4.3 Study procedures

The study starts as soon as ethical approval is obtained, preferably in calender week 15 2020. The rapid study start is intended in order to capture as many COVID-19 cases as possible. The study will be ongoing until the COVID-19 pandemic is eradicated, a vaccine or curative therapy has become available, or if the Investigators come to the decision to terminate the study. Due to the unclear course of the pandemic, it is not possible to provide an exact date of study duration. We anticipate that the study should be terminated on 31st December 2021 the latest.

First, study participants will be contacted by mail with the study information and the informed onsent sheet. After providing informed consent (in case of questions, the study staff can be contacted for questions at the contact information already known to the study participants) the study participants, baseline clinical information is provided in a study questionnaire. The study participants will then obtain an AVA bracelet, either by post or in the study center. Informed consent will be discussed personally on the occasion of a personal contact due to provision of the AVA bracelet or presentation for blood sampling.

While the AVA Bracelet was designed to measure physiological changes across the menstrual cycle. its sensors work across genders and age groups. We foresee that the device is capable of providing relevant insights for men and women alike during this pandemic, including among those populations most at risk of developing serious complications from COVID-19, including: people over the age of 60 and people with underlying conditions like hypertension, diabetes, cardiovascular disease, chronic respiratory disease, and cancer. The AVA bracelet automatically saves physiological information every 10 seconds throughout the night, requiring at least 4 hours of relatively uninterrupted sleep each night to stabilize parameter measurements. The wrist-worn bracelet acts as a data logger, recording and storing user's physiological sensors signals as raw datasets throughout the night. Currently, the user synchronizes the bracelet to the mobile phone application the following morning. The mobile app reads the raw datasets via Bluetooth Low Energy (BLE) and transfers them to the backend. After computation and preprocessing of the physiological parameters based on the bracelet's recordings, an algorithm obtains pre-processed physiological parameters changes that are transferred back to the mobile app and displayed to the user.

Designed to combine multiparameter measurement into one device, the AVA bracelet could leverage its real-time monitoring system to fight a novel health threat. We believe the simple but continuous monitoring of temperature, breathing and pulse rates could provide guidance around if and when people should seek medical care. Furthermore, the recorded physiological data could improve our knowledge of COVID-19's early signs and overall trajectory.

Figure 1: Illustration of the AVA bracelet

The AVA bracelet is intended to monitor a woman's fertility by measuring and recording physiological parameters (body temperature, resting pulse, heart rate variability, and breathing rate) as an aid in ovulation prediction to aid in conception (not to be used for contraception). Its intended use is to measure and display physiological parameters to aid women in ovulation prediction to facilitate conception. Additionally, parameters are collected to improve the quality of the prediction and to provide general information on health and wellness. The device is CE-marked (certificate see Appendix 2).

We will obtain COVID-19 specific information at baseline and study participants will asked to provide COVID-19 specific symptoms during the study duration. In case of the occurrence of COVID-19 specific symptoms, participants will be asked to undergo RT-PCR and serological testing according to national guidelines by utilizing routine healthcare. We will conduct periodic surveys (e.g. every 14 days) requesting the study participants to provide information regarding their health status. Study participants will be asked to provide a blood sample at the end of the study for serological studies of COVID-19 (investigation of SARS-CoV2-antibodies). The flowchart of the participant journey within the present investigation is summarized in Figure 2. A summary of the study visits is provided in Appendix 1.

Figure 2: Journey of study participants.

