3.2 Primary and secondary endpoints

Primary endpoint is the occurrence of COVID-19 infection, as assessed by clinical signs, serology and/or RT-PCR testing Date of occurrence, clinical symptoms and laboratory results, how infection was diagnosed is collected to describe the primary endpoint. The endpoints will be collected by periodic reports obtained on questioning the study participants. Participants and the

treating healthcare institutions will be contacted to obtain respective information.

As a secondary endpoint severity of COVID-19 infection will be assessed. Participants and the treating healthcare institutions will be contacted to obtain respective information. The following parameters will be collected: Hospitalization needed within 30 days of COVID-19 diagnosis (including timing)? ICU admission within 30 days of COVID-19 diagnosis (including timing)? Use of mechanical ventilation within 30 days of COVID-19 diagnosis (including timing)? Participant reported health status after COVID-19 diagnosis (including timing)? COVID-19 related mortality? Quantiative RT-PCR results (viral loads) and quantitative Immunoassay results of COVID-19 specific laboratory markers? Results of other respiratory pathogens in COVID-19 negative participants available? Further healthcare contact of patients tested negative for COVID-19?

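### Participants see their nightly readings while they report the symptoms and start the tests behind the endpoint, so symptom-onset dates and the detection of dated, symptom-triggered cases are open to bias of unknown size

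*Protocol*

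**What the plan says.** **What the participant sees.** Under protocol 4.3, "the user synchronizes the bracelet to the mobile phone application the following morning", and then an algorithm produces "pre-processed physiological parameters changes that are transferred back to the mobile app and displayed to the user". Section 2 describes the same data flow. No section turns the display off for participants.

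**What the participant reports.** Section 3.2 defines the primary endpoint as "occurrence of COVID-19 infection, as assessed by clinical signs, serology and/or RT-PCR testing", with a date of occurrence and the way the infection was diagnosed. It states: "The endpoints will be collected by periodic reports obtained on questioning the study participants". Treating institutions are also contacted. Under 4.3, "study participants will asked to provide COVID-19 specific symptoms during the study duration", with surveys given as, for example, every 14 days.

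**What starts a test.** Under 3.4 and 4.3, RT-PCR and interim serology follow symptoms and run through routine care under national guidelines.

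**What does not depend on the participant's symptoms.** The synopsis plans serology for all at the beginning and end of the study, and Appendix 1 lists sampling at bracelet distribution and at the final visit. Sections 3.4 and 4.3 repeat the end-of-study sample.

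**What the study wants to show.** Section 3.1 asks whether the bracelet identifies infection before clinical illness, and hypothesises that changes in the parameters come before symptoms.

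**The concern.** The hypothesis in 3.1 compares two dates: the night on which the parameters change and the day on which symptoms begin. The second date comes mainly from a person who may already have seen the first. Someone who notices raised values may look for symptoms, date them to that morning and go for a test. An infected person with unremarkable values has less reason to do so.

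Two quantities are exposed, in opposite directions.

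- **Sensitivity among dated cases.** If abnormal readings prompt testing, infections with abnormal readings are over-represented among the cases that get a date. Apparent sensitivity then tends to rise.
- **Lead time.** If abnormal readings prompt early reporting, the onset date moves toward the abnormal night. Observed lead time then tends to shrink.

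These do not cancel, because they are different quantities. Nor is this something the analysis plan can settle later. If nobody records whether a reading prompted a report, prompted and unprompted cases cannot be told apart.

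**Working it through.** The protocol gives no target sensitivity, lead time or testing rate, and its sample size of 2170 is simply the existing cohort. There is no figure to reproduce. Every input below is an assumption chosen to show direction and rough scale.

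**1. Sensitivity among symptom-tested cases.** Let *s* be true sensitivity, *r1* the chance that an infected person with abnormal readings is tested, and *r0* the chance with normal readings.

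Apparent sensitivity = *s·r1* / [*s·r1* + (1 − *s*)·*r0*]

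| True *s* | *r1* | *r0* | Calculation | Apparent |
|---|---|---|---|---|
| 0.50 | 0.80 | 0.60 | 0.40 / (0.40 + 0.30) | 0.571 |
| 0.50 | 0.90 | 0.50 | 0.45 / (0.45 + 0.25) | 0.643 |
| 0.40 | 0.80 | 0.60 | 0.32 / (0.32 + 0.36) | 0.471 |
| 0.40 | 0.90 | 0.50 | 0.36 / (0.36 + 0.30) | 0.545 |

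If *r1* = *r0*, apparent sensitivity equals true sensitivity.

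**2. The same inputs with end-of-study serology for everyone.** If serology finds a share *d* of the infections not already tested, each *r* becomes *r* + (1 − *r*)·*d*. For *s* = 0.50 and *d* = 0.80:

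- 80% v 60% becomes 0.96 v 0.92, so 0.48 / (0.48 + 0.46) = 0.511.
- 90% v 50% becomes 0.98 v 0.90, so 0.49 / (0.49 + 0.45) = 0.521.

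At *d* = 0.50 the results are 0.529 and 0.559. At *d* = 1 both are exactly 0.50. So for the question of whether a person was ever infected, a sensitive antibody test with good attendance removes most of the distortion.

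**3. Why serology does not rescue the early-detection question.** The planned first-in and last-out dates are 12 April 2020 and 31 December 2021, more than 20 months apart. Seroconversion between two samples that far apart does not say which nights preceded the illness. A case found only at the final visit cannot count as detected before symptoms. Cases with a usable date come mainly from the symptom-triggered route, where step 1 applies.

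**4. Lead time.** Take lead time as reported onset minus first abnormal night, with true mean *L*. If a share *q* of cases is prompted by the display to report *k* days after that night:

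Mean observed lead = (1 − *q*)·*L* + *q·k*

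| *L* (days) | *q* | *k* = 0 | *k* = 1 |
|---|---|---|---|
| 3 | 0.10 | 2.7 | 2.8 |
| 3 | 0.25 | 2.25 | 2.5 |
| 3 | 0.50 | 1.5 | 2.0 |
| 2 | 0.10 | 1.8 | 1.9 |
| 2 | 0.25 | 1.5 | 1.75 |
| 2 | 0.50 | 1.0 | 1.5 |

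With *q* = 0 the true lead is recovered.

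**The case against.** The strongest reply has five parts.

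- **Serology is part of the endpoint and is planned for all.** This stands for ever-infected status (step 2). It does not stand for the onset date.
- **The testing gap is not all due to the display.** Section 3.1 expects the parameters to change because of infection, and heart rate variability to reflect its severity. People with abnormal readings would then be sicker and tested more often with a blank screen too. This stands. Of the excess in step 1 (57% or 64% against 50%), the display may account for anything from none to all, so those figures do not measure what hiding the values would gain.
- **The app shows inputs, not the test result.** The algorithm is still to be trained, and no COVID-19 alert is described. This stands and may weaken the effect. A reader might infer that the index test drives its own reference standard; the protocol does not go that far.
- **The passage on seeking care is forward-looking.** The text that monitoring "could provide guidance around if and when people should seek medical care" describes the device's potential and is not a study instruction. It shows that the authors find such an effect plausible, and no more than that.
- **There are other sources.** Treating institutions, laboratory results and the mode of diagnosis are collected too. This helps, but institutions know only the people who sought care.

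**Conclusion.** The point holds as a weakness in how dates and symptom-triggered cases are collected. The display, the self-report, the symptom-triggered tests and the absence of any record of prompting all follow from the text. The effect on behaviour is not shown by any figure in the protocol, so the size of the bias is unknown and could be nil.

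A reader might infer that the bracelet's accuracy will be biased, or that the trial would report 57% or 64% where 50% is true. The documents do not support either. Those values, and 47% and 55% for a true 40%, rest on assumed testing rates and apply only to symptom-tested cases. With end-of-study serology finding 80% of the remaining infections, the first pair falls to about 51% and 52% for ever-infected status.

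What remains exposed is the primary question of early detection, because it needs a dated onset. On assumed values, a 3-day lead could be observed as anything from 2.8 down to 1.5 days.

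**What to change.** In 4.3 and in the symptom and 14-day questionnaires:

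1. Add one item: did a bracelet reading prompt this report or test, and if so on what date?
2. Where the app allows, ask for symptoms before that night's values are viewed.
3. Have existing staff confirm endpoint status and onset date without access to bracelet data.
4. Report early-detection accuracy and lead time with and without reading-prompted cases. The detail of this analysis can sit in the analysis plan, but it needs item 1 in the data.

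Hiding the values until study end is worth considering only if it is technically possible and compatible with the regulatory basis. Section 4.3 gives display of the parameters as part of the device's intended use, and the synopsis bases Category A on the CE mark and intended use. No section says that the display can be switched off.

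The cost is one extra questionnaire item, a restriction on what the confirming staff can see, and a small additional analysis. Hiding values could also cost some participant engagement. None of this changes who is tested or when.

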4.4 Withdrawal and discontinuation

If a study participants withdraw from the study, recording of AVA bracelet data will be stopped. Data is stored in a coded manner and the decoding information for concerned individuals will be

irreversibly destroyed.

5 STATISTICS AND METHODOLOGY

5.1. Statistical analysis plan and sample size calculation

Together with [name] and her team, data will be analysed by machine learning procedures. By training models, we aim to identify characteristic patterns of the recorded physiological parameters in order to predict the occurrence of COVID-19 infection. We intend to employ software packages such as R or SAS for modeling.

The present study is an (non-funded) associated partner to the COVID-RED consortium, which applied for a Horizon 2020 grant (see grant application as a document accompanying the present study protocol. Depending on the realization of that project, we will contribute data to that joint project.

The sample size of 2170 is given by the already existing study population. At a later stage, we may think of enlarging the sample size to 5000 by offering non-GAPP participants a participation in the study. However, this would be subject of a protocol amendment.

5.2. Handling of missing data and drop-outs

Should participants not regularly record data with the AVA bracelet, cases will be excluded from further analysis.

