Objective(s):	Primary objective A.) To see whether the AVA bracelet is capable to reliably identify persons with COVID19 infection early, before they get clinically. This would allow for early isolation and testing of contact persons, thereby preventing extensive spreading of the Virus. When reversing the process of lockdown of social and economic systems or during a so called second wave of the COVID-19 pandemic, the AVA bracelet could serve as a sensitive tool to observe relapsing infection rates.
	Secondary objective
	a.) To see whether the AVA bracelet would serve to recognize severe cases early allowing for risk stratification, early treatment and allocation of adequate care to patients with COVID19.
	b.) To obtain a seroprevalence of COVID19 affected cases in the population of Liechtenstein.
Outcome(s):	Occurrence of COVID-19 infection, Severity of COVID-19 infection.
Study design:	Observational population-based cohort study employing a CE-marked medical device.
Inclusion / Exclusion criteria:	Inclusion criteria: participant of the GAPP study. Exclusion criteria: Inability to provide informed consent.

Measurements and	Serological status for SARS-CoV2-antibodies will be determined at the beginning and the end of the study.			
procedures:	The participants will be asked to answer a questionnaire about recent infections at study entry, undergo baseline serological testing. Study participants will be monitored overnight with the employed fertility tracker. We will collect information about clinically documented infections in all participants during follow-up, and provide serology at the end of the study.			
	The study and participant recruitment will be performed within the study organization of the GAPP study, an ongoing prospective follow-up study. Baseline characteristics and other clinical information will be used from the GAPP study database.			
Study Product / Intervention:	The fertility tracker automatically saves physiological information every 10 seconds throughout the night, requiring at least 4 hours of relatively uninterrupted sleep each night to stabilize parameter measurements. The wrist-worn bracelet acts as a data logger, recording and storing user's physiological sensors signals as raw datasets throughout the night. Currently, the user synchronizes the bracelet to the mobile phone application the following morning. It is planned that participants wear the fertility tracker overnight during the study period.			

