Control Intervention (if applicable):	Not applicable			
Number of Participants with Rationale:	Participants of the ongoing population based GAPP cohort study conducted in Liechtenstein will be included (n=2170; study approved by KEK ZH StvNr. 66/09). These will receive the AVA bracelet for free. We eventually might attain a sample size of 5000 participant by onboarding additional participants. For this second phase, we will seek separate ethical approval.			
Study Duration:	The course of the pandemic can currently not be predicted and is critical for the duration of the study. WE anticipate a duration of nearly 3 years.			
Study Schedule:	Participants should be included as fast as possible, in order to catch as many endpoints during the COVID-19 pandemic.			
	Planned 12/04/2020 of First-Participant-In			
	Planned 31/12/2021 of Last-Participant-Out			
	Depending on the course of the pandemic, the study can be terminated earlier.			
Investigator(s):	[name].med. [name], McMaster University, Hamilton ([contact]), Dr.med. [name], Private University Liechtenstein, Triesen ([contact]), [name], Universität Basel ([contact]), [name] MSc, Private University Liechtenstein ([contact]), Dr.[name] PhD, Chief medical Officer AVA for women ([contact])			
Study Centre(s):	Single-centre study. GAPP-Studie c/o labormedizinisches zentrum [name], [name]			
Statistical Considerations:	Prediction of the development of COVID-19 infection will be modeled on the base of nightly monitoring of temperature, breath rate, pulse rate and movements by means of machine learning methods. Algorithms will be trained by comparing monitoring data of COVID-19 diseased and non-diseased individuals by a big data approach employing machine learning. The project partner AVA for women has already used such an approach to predict fertile days in women with a higher than 90% accuracy. The seroprevalence of COVID-19 will be presented as count (percentage) and we			
	will standardize these numbers to the general population of the Principality of Liechtenstein. The sample size is given by the sample size included in the GAPP study.			
GCP Statement:	This study will be conducted in compliance with the protocol, the current version of the Declaration of Helsinki, ISO EN 14155 as well as all national legal and regulatory requirements.			

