3 STUDY OBJECTIVES AND DESIGN

3.1 Hypothesis and primary objective

We hypothesize that by monitoring temperature, breath rate, pulse rate, and movements, it is possible to predict the occurrence of COVID-19 infection. We hypothesize, that temperature will increase due to inflammation/infection, breath rate will increase due to subclinical affection of lungs by COVID-19, heart rate variability as an indicator of stress will be diminished both as a consequence of infection also reflecting severity of infection. Further, we anticipate that registration of characteristic movements also allows to recognize cough. Fever, breathing problems, and cough are all clinical cornerstones in the diagnosis of COVID-19 infection. WE further hypothesize that the alterations in measured parameters antecede the occurrence of clinical symptoms.

Primary objective

A.) To see whether the AVA bracelet is capable to reliably identify persons with COVID19 infection early, before they get clinically. This would allow for early isolation and testing of contact persons, thereby preventing extensive spreading of the Virus. When reversing the process of lockdown of social and economic systems or during a so called second wave of the COVID-19 pandemic, the AVA bracelet could serve as a sensitive tool to observe relapsing infection rates.

Secondary objective

- a.) To see whether the AVA bracelet would serve to recognize severe cases early allowing for risk stratification, early treatment and allocation of adequate care to patients with COVID19.
- b.) To obtain a seroprevalence of COVID19 affected cases in the population of Liechtenstein.

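### Section 5.2 excludes irregular bracelet wearers from all further analysis, with no threshold, window or limit by objective; it should apply only to bracelet-based analyses

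*Protocol*

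**What the plan says.** The whole of Protocol section 5.2 reads "Should participants not regularly record data with the AVA bracelet, cases will be excluded from further analysis". Regular recording is not defined, no period is named over which it is judged, and no objective is exempted.

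The outcomes are collected without the bracelet:

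- **Infection** (section 3.2): "Primary endpoint is the occurrence of COVID-19 infection, as assessed by clinical signs, serology and/or RT-PCR testing". The information comes from periodic questioning and from contact with participants and treating institutions.
- **Severity** (section 3.2): events such as "Hospitalization needed within 30 days of COVID-19 diagnosis (including timing", ICU admission, ventilation and death, from the same sources.
- **Seroprevalence** (section 3.1): "To obtain a seroprevalence of COVID19 affected cases in the population of Liechtenstein". The synopsis gives the data source as "Serological status for SARS-CoV2-antibodies will be determined at the beginning and the end of the study" and adds that the investigators "will standardize these numbers to the general population of the Principality of Liechtenstein". It mentions no adjustment for exclusion by wear.

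On the device, the synopsis describes it as "requiring at least 4 hours of relatively uninterrupted sleep each night to stabilize parameter measurements" and says that the user synchronises it with the phone each morning. Section 3.4 asks for nightly wear until the study ends, which section 4.3 puts at 31 December 2021 at the latest. Section 6.1.1 names device dysfunction as a reason for missing recordings.

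**The concern.** The rule makes inclusion depend on behaviour after enrolment, and that behaviour may be affected by the outcome. Three things are at stake.

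1. **Needless loss.** Serology, infection and severity information from irregular wearers would be set aside although it is valid without any recording.
2. **Loss of the data that matter most.** The primary objective is detection before clinical illness. With no window in 5.2, a participant with complete nights before onset who stops wearing the device during or after illness can be excluded because of what happened later.
3. **Possible selection on outcome.** A night with poor sleep, or one followed by no synchronisation, may not yield usable data. Someone in hospital or on ventilation may be unable to wear or synchronise the device. If infected or severely ill participants are retained at a different rate from the others, the estimates shift.

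The word *cases* in 5.2 is also ambiguous. If it means participants, all three points apply. If it means COVID-19 cases, exclusion depends directly on the outcome.

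**Working it through.** **The plan's own figure.** There is none to reproduce. Section 5.1 says "The sample size of 2170 is given by the already existing study population", and no precision, power or drop-out rate is attached to it.

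**Step 1: which objectives need the bracelet.**

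| Objective | Data needed | Bracelet needed? |
|---|---|---|
| Early detection (primary) | Nights before onset, plus infection status | Yes, for the nights before onset |
| Early recognition of severe cases | Nights, plus severity events | For the prediction, yes; for counting events, no |
| Infection count | Clinical signs, serology, RT-PCR | No |
| Seroprevalence | Blood sample | No |

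The exclusion in 5.2 covers all four rows.

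**Step 2: seroprevalence.** Let p be the true prevalence, and r1 and r0 the shares of infected and uninfected participants that the rule keeps. Then

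observed prevalence = p·r1 / [p·r1 + (1 − p)·r0].

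N = 2170 is from section 5.1, taking everyone as sampled. The values p = 5%, r1 and r0 are assumptions.

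| r0 | r1 | Calculation | Observed | Relative bias |
|---|---|---|---|---|
| 0.8 | 0.8 | 0.040 / 0.800 | 5.0% | 0% |
| 0.8 | 0.7 | 0.035 / 0.795 | 4.4% | −12% |
| 0.8 | 0.6 | 0.030 / 0.790 | 3.8% | −24% |
| 0.8 | 0.4 | 0.020 / 0.780 | 2.6% | −49% |
| 0.7 | 0.8 | 0.040 / 0.705 | 5.7% | +13% |

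Relative bias is nearly the same at p = 2% and p = 10%. The last row shows that the direction reverses if infected people record better.

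**Step 3: precision when retention is equal.** The standard error is √[p(1 − p)/n]. With n = 2170 it is √(0.0475/2170) = 0.47 percentage points. With n = 0.8 × 2170 = 1736 it is √(0.0475/1736) = 0.52 points. So even without bias, precision is lost for no gain.

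**Step 4: severity.** The same formula applies among infected participants. Assume a true severe share of 10% and 80% of mild cases retained. Retaining 80%, 60%, 40% or 20% of severe cases gives an observed share of 10.0%, 7.7%, 5.3% or 2.7%. For example, at 40%: 0.04 / (0.04 + 0.72) = 5.3%.

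**Step 5: why each case counts.** At the incidence quoted in section 4.2 (1582 per million), the cohort would hold 2170 × 1582 / 1,000,000 = 3.4 cases. More would be expected as the pandemic continued, but cases may be few, and a lost case with good pre-onset recordings is costly.

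**The case against.** A reader might infer that the rule removes people because they are ill and so biases every objective. The documents do not support that.

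- No section says that illness causes irregular recording. Device failure and ordinary non-adherence are also causes.
- From 12 April 2020 to 31 December 2021 is about 628 nights. If 14 to 30 nights were lost to COVID-19 (assumed), that is 14/628 = 2% to 30/628 = 5%. A participant judged over the whole follow-up would still be a regular recorder. Exclusion driven by illness needs a short assessment window or follow-up that ends with the illness, and 5.2 specifies neither.
- With equal retention by infection status, seroprevalence is not biased at all.

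A reader might also infer that detection sensitivity would be overstated by 8 to 24 points: 0.80 × 0.90 = 0.72 and 0.80 × 0.70 = 0.56, against 0.80. The protocol states no sensitivity for COVID-19, and both the 80% and the 10% to 30% excluded are assumed. Counting excluded cases as undetected answers a different question, namely performance in the whole cohort. It does not show that the estimate among wearers is wrong, and some restriction to people with recordings is unavoidable when training an algorithm.

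Finally, 5.2 follows directly on 5.1, which describes only the modelling of recorded parameters, so a narrower intention is plausible. Definitions of a valid night may also sit in an analysis plan that is not at hand.

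These points limit the claim about bias. They do not repair the sentence itself. It sets an exclusion of unlimited scope, and a narrower intention would need to be written down.

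**Conclusion.** The point stands as a fault in a rule that the protocol states. Read as written, 5.2 needlessly removes participants from seroprevalence and from the infection and severity counts, and it allows usable pre-onset recordings to be discarded because of later non-wear. That much follows from the text alone.

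Bias is a risk of unknown direction and size. It depends on whether retention differs by infection status or severity, on which the protocol gives no figure. Under the assumed rates, a true seroprevalence of 5% could appear as anything from 2.6% to 5.7%. The certain cost is precision: a standard error of 0.52 instead of 0.47 points if 80% are retained evenly. If seroprevalence uses every serology result regardless of wear, the bias from this rule is zero by construction.

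**What to change.** Reword section 5.2 as follows.

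1. Apply the recording requirement only to analyses that use bracelet data.
2. Exclude unusable nights, not participants.
3. For cases with a known onset or diagnosis date, judge eligibility on usable nights in a fixed window before that date. Apply the same window at matched calendar dates to non-cases. Handle seroconverters without an onset date separately, since no such window can be placed for them.
4. Keep every consenting participant with a serology result or endpoint information in the seroprevalence, infection and severity summaries.
5. Report the number and characteristics of those excluded from the bracelet analyses, by infection status and severity.
6. As a supplementary analysis, labelled as a different estimand (use in the whole cohort), count dated confirmed cases without usable pre-onset nights as not detected.

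The cost is protocol wording and a little more analysis. The whole-cohort detection figure may look less favourable than the figure among wearers.
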